1.2 Hypotheses and Endpoints

Hypotheses

- 1) Use of a 22 G preloaded needle for EUS guided fiducial marker placement in patients with pancreatic cancer will be delivered in at least 60% of the procedure time that it takes for traditional back-loaded 22G needles, improving overall procedure efficiency.
- 2) Use of a 22 G preloaded needle for EUS guided fiducial marker placement in patients with pancreatic cancer will maintain comparable technical success and adverse event rates when compared to traditional back-loaded 22G needles.

Primary Aims

1) To compare the procedure time of 22G needle placement of three Visicoil fiducial markers and 22G needle preloaded fiducial markers.

Secondary Aims

1) To compare endpoints of technical success defined as proper placement of three fiducial markers in a pancreatic neoplasm in 22G needle placement of Visicoil fiducial markers and 22G needle preloaded fiducial markers.

2) To compare adverse event rates in 22G needle placement of Visicoil fiducial markers and 22G needle preloaded fiducial markers

1.3. Preliminary Studies/Progress Report: To date, there are no preliminary studies of the above proposed study.

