2. RESEARCH DESIGN AND METHODOLOGY

A. Description of Population to be Enrolled. (Appendix AP1)

Inclusion Criteria:

• Patients with pathologically confirmed pancreatic cancer referred for IGRT.

Exclusion Criteria:

- Age <18
- Inability to consent
- Known coagulopathy/thrombocytopenia (INR >1.5, platelets <75)
- Patients on antiplatelet/anticoagulant medication that cannot safely be discontinued 5-7 days prior to the procedure
- Gold allergy
- Current infection
- EUS evidence of vessel interfering with path of fiducial marker
- Pregnancy

B. Study Design and Research Methods: Patients with pancreatic cancer referred for fiducial marker placement for IGRT will be eligible for enrollment in the study. Eligibility of study enrollment will be determined prior to the endoscopic evaluation. Subjects will be contacted via telephone before their scheduled visit to inform the subject about the study with a copy of the consent form sent to the subject prior to the EUS procedure (please see Appendix AP2 for copy of phone script). The consent form will then be reviewed in person either in the pre-operative endoscopy unit or in the gastrointestinal clinic if pre-procedure consultation was obtained. Prior to the patients undergoing EUS evaluation, patients will be excluded from the study if they meet any of the exclusion criteria as listed above. All patients who are not excluded from the study as outlined above will be eligible for the study.

Patients without a previous diagnosis of pancreatic cancer but are referred for EUS guided FNA of a suspicious for pancreatic malignancy may also be eligible if a diagnosis of pancreatic cancer can be made by an on-site by a cytopathologist, and the stage dictates that they will need IGRT based on clear discussion with the radiation oncologist, oncologist and surgeon. In this situation fiducial markers may be placed in the same setting.

DESCRIPTION OF THE PROCEDURE (Fig. 1)

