Once the patient is consented for the study, randomization will then be performed using stratified (based on location of the tumor – head/neck vs. body/tail) block randomization. The patients will undergo Linear EUS, as previously described by Devila Fejardo et al. and have fiducial marker placement via a traditional 22G back-loaded needle (Visicoil) [22] or the new 22G preloaded needle (PreLoad4). Multiple endpoints will be recorded, including total length of procedure, how many markers are successfully deployed, and technical success (Ease of passage of delivery system, ease of deployment of fiducials, EUS visualization of delivery system needle, EUS visual appearance of fiducials, and time for fiducial placement defined as starting time of removing the needle from its packaging and ending time as removal of needle after final marker deployment). Procedure time will be recorded by a research assistant at each site. Fiducial marker location will be confirmed via fluoroscopy at time of placement and on 4D treatment planning CT ordered by the radiation oncologist for simulation.

Patients will be discharged home after post procedure recovery. Patients will be contacted at home by a research coordinator or endoscopy staff 24-48 hours and 7-10 days after the procedure to document any

immediate and delayed complications. Patients will return for their IGRT visit, and any evidence of fiducial marker migration will be recorded by the radiation oncologist.

For patients who have preceding diagnostic FNA, this will be recorded, with number of passes/aspiration attempts recorded as well.

Endpoints

Primary endpoints utilized in this study will be:

• To compare procedure time of 22G needle placement of three Visicoil fiducial markers and 22G needle preloaded fiducial markers.

Secondary endpoints will include:

- Technical success of fiducial marker placement in 22G back-loaded needles and 22G preloaded needles defined by proper placement of three fiducial markers in a pancreatic neoplasm.
- Rate of fiducial migration
- Ease of passage of delivery system
- Ease of fiducial deployment
- EUS visual appearance of fiducials
- Visualization as assessed by radiation oncology
- Inadvertent deployment of fiducials
- Adverse event rates recorded throughout the study period
- Descriptive comparison of outcomes across sites

Figure 1- Proposed Study Methods

C. Description, Risks, and Justification of Procedures and Data Collection Tools.

Recording of Complications

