Factors that could threaten our ability to obtain meaningful generalizable knowledge from this study would be lack of patient followup to reevaluate fiducial marker location. However, as patients are having this procedure performed for cancer therapy, it is unlikely that there will be a large proportion of patients who are lost to followup.

E. Data Analysis Plan. This section should include:

For Quantitative analyses:

i) Statistical Analysis: Categorical variables will be summarized with counts and percentages whereas continuous covariates will be summarized with means and standard deviations (SD). For evaluation of the demographic data a Fisher's exact test or Mann-Whitney U test will be performed as applicable.

ii) Success rates for each of the two arms will be calculated as a proportion of number of successfully deployed fiducial markers over the total number of patients in whom this was attempted within the study population. This will be reported as a percentage. Comparison of successful deployment of fiducial markers by two comparative groups will be performed by Fisher's exact test. Similarly, comparison between the two arms will be performed for technical success, procedure time, adverse event rate, rate of migration, ease of fiducial deployment, and visualization of needle and fiducials via EUS and CT by using Fisher's exact test. When data is ordinal, comparisons will be made using Mann-Whitney U test.

Sample Size:

Sample size calculated for the primary aim showed that in order to detect that the PreLoad4 device can be delivered in at least 60% of the time it takes to deliver a fiducial marker by back-loading, for an 80% power and alpha of 0.05 (two-sided) a minimum of 20 patients will be required in each arm.

Randomization:

Patients will undergo central block randomization (5 blocks of 4 per stratified arm at each center) stratified based on tumor location (head/neck vs. body/tail). This will be performed by a computerized binary number generator at the University of Colorado, who will control randomization for all sites. The arm that the patient will be randomized to will be determined by the above process and with the use of opaque sealed envelopes.

F. Summarize Knowledge to be Gained.

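### The deployment success rate in protocol 2.E ii) divides markers by patients, so it reads 100% at one third of planned markers and 300% at full success

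*Protocol*

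**What the plan says.** Protocol section 2.E ii) gives one formula for a success rate. In each arm it is a "proportion of number of successfully deployed fiducial markers over the total number of patients in whom this was attempted", expressed as a percentage. The next sentence reads "Comparison of successful deployment of fiducial markers by two comparative groups will be performed by" Fisher's exact test. The text then goes on: "Similarly, comparison between the two arms will be performed for technical success, procedure time" and several other outcomes, again by Fisher's exact test, with the Mann-Whitney U test for ordinal data.

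Technical success has its own definition. Section 1.2 refers to "technical success defined as proper placement of three fiducial markers in a pancreatic neoplasm in 22G needle placement", and the secondary endpoints in section 2.B repeat that it is "defined by proper placement of three fiducial markers in a pancreatic neoplasm". Each patient either meets that definition or does not. The procedure description in section 2.B keeps the marker count apart from it: "Multiple endpoints will be recorded, including total length of procedure, how many markers are successfully deployed, and technical success".

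The SAP names chi-square or Fisher's exact test for categorical data, states intention-to-treat for all analyses and adds a per-protocol analysis. It gives no numerator or denominator for any success rate.

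**The concern.** A proportion needs a numerator that is a subset of its denominator. Here up to three markers are counted for each patient, and each patient counts once below the line. The result is an average number of markers per patient, so calling it a percentage misstates it.

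Two things are at stake. A reader who sees 100% will take it as complete success when it means one marker per patient on average. Such a figure also cannot be read beside the deployment success of 95.6% that section 1.1 cites from the porcine study.

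Second, the rate does not say whether the Fisher comparison counts patients or markers. Whoever runs the analysis must choose, possibly after seeing the data, and the choice can change the result.

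**Working it through.** The plan gives no numeric value for this rate, so there is no figure to reproduce. Its one computed figure, 20 per arm, concerns procedure time and is used here only as an input.

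**Inputs.** Patients per arm: n = 20 (protocol 2.E, Sample Size; SAP). Markers per patient: 3 (Protocol Summary; sections 1.2 and 2.B). Planned markers per arm: 3 × 20 = 60. I assume that placement is attempted in all 20 patients and that no more than three markers are counted in any patient.

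**Step 1: the rate as written.** With m markers deployed, the written rate is m/n and the share of planned markers is m/(3n). The written rate is therefore always three times that share, whatever n is.

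| Markers deployed (m) | Written rate, m/20 | Share of planned, m/60 | Patients minus markers, 20 − m |
|---|---|---|---|
| 10 | 50% | 16.7% | 10 |
| 20 | 100% | 33.3% | 0 |
| 40 | 200% | 66.7% | −20 |
| 57 | 285% | 95.0% | −37 |
| 60 | 300% | 100% | −40 |

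**Step 2: Fisher cells.** Fisher's exact test needs successes and failures in the same unit. If the written numerator is taken as successes and the written denominator as the total, the failure cell is 20 − m. It is negative once there is more than one marker per patient on average, and software rejects the table. Below that point the cell is not negative, but it has no meaning: 10 markers could come from ten patients with one each or from four patients (3 + 3 + 3 + 1).

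**Step 3: the ratio does not give the patient-level result.** Forty markers in 20 patients reads 200% in both of these cases:

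- Every patient has two markers (20 × 2 = 40), so 0/20 have all three.
- Thirteen patients have three and one has one (13 × 3 + 1 = 40), so 13/20 have all three.

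**Step 4: why the unit must be named.** Suppose that one arm deploys every marker, and that in the other arm two patients receive none (2 × 3 = 6 markers missing). The written rates are 60/20 = 300% and 54/20 = 270%. Two ways of repairing the comparison then give different results:

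- By patient with all three deployed: 20/0 against 18/2, two-sided Fisher p = 0.49.
- By marker: 60/0 against 54/6, two-sided Fisher p = 0.027.

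The second treats the three markers in a patient as independent. In this example all six failures come from two patients, so that assumption is plainly false. The example is an illustration and does not predict the trial's data.

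**The case against.** The strongest reply is that this is a slip in one line with little effect. Technical success is defined per patient and named for its own comparison, so the question in Hypothesis 2 does not depend on this formula. Marker deployment is not on the list of secondary endpoints in section 2.B; it appears only among the items recorded. Where three markers are planned for every patient, dividing the written rate by three gives the share of planned markers. All of this stands, and it limits the weight of the point.

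It can also be said that the Fisher sentence does not state that its cells come from the rate. That is correct. The number of markers deployed is recorded for each patient, so a valid table can be built from the data, and the Mann-Whitney rule for ordinal data could cover a count from 0 to 3. A reader might infer that no Fisher test of deployment is possible; the documents do not support that. What fails is a table built from the numerator and denominator that the plan writes down, and the plan offers no others for deployment.

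A reader might also infer that technical success, Hypothesis 2 or the trial's main conclusion is compromised. The documents do not support that either: the patient-level definition is intact, and neither the procedure-time endpoint nor the sample size uses this rate.

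The reply does not remove the need for a correction. Following 2.E ii) literally gives an invalid percentage, and nothing in section 2.B or the SAP replaces it.

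**Conclusion.** The point holds as a unit error in a secondary deployment rate. As written, the rate is three times the share of planned markers deployed: 100% at 20 of 60, and 300% at 60 of 60. It is a mean count per patient, and its two components cannot fill a Fisher table. The multiple of three rests on three planned markers per patient and on placement being attempted in every patient. It does not depend on there being 20 per arm.

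The error should be corrected because leaving the unit open allows a choice after the data are seen, and Step 4 of the working shows that this choice can matter. It does not threaten the primary analysis. The documents do not show which unit was used in practice, so nothing here implies that a reported result is wrong.

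**What to change.** State one unit in protocol 2.E ii) and repeat it in the SAP.

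- **Deployment, for the Fisher comparison:** patients with all three markers successfully deployed, divided by patients in the arm. Use intention-to-treat as the SAP states, with its per-protocol analysis as support.
- **Technical success:** keep proper placement of three markers as its own patient-level rate. Deployment and proper placement should not be merged.
- **Marker-level rate, if wanted:** deployed markers divided by planned markers (three per patient). Report it descriptively or with a method that allows for clustering within patient. Do not apply a Fisher test that treats markers as independent.

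The cost is a few lines of text, since the number of markers deployed is already recorded. There are two drawbacks. An all-three rule discards information on partial deployment, which the descriptive marker rate can show. The definition of the deployment rate also changes, including its denominator, which moves from patients attempted to patients in the arm. The SAP is written in the past tense, so the analysis may already be complete. In that case, report the numerator, denominator and unit actually used, and label any change as post hoc.

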## Statistical Analysis Plan

The sample-size calculation was based on limited experimental data in a porcine model, and on a consensus decision among expert endosonographers regarding the relative reduction in the time (60%) to deploy preloaded fiducial markers. We estimated that a sample size of 40 patients (20 in each arm) was needed to provide the study with at least 80% power and a 2-sided alpha of 0.05. All analyses were performed according to the intention-to-treat principle. Per-protocol analysis was also performed. Descriptive statistics are reported as absolute values (percentage), mean 2 standard deviation, and median (IQR), as appropriate. Comparisons of baseline characteristics and outcomes were evaluated using chi-square or Fischer exact test for categorical data and Student t test or Mann-Whitney U test for continuous data. Pre-established subgroup analysis was performed by tumor location (head/neck vs body/tail). Although not pre-established in the study protocol, results were also stratified by time of randomization (first half vs second half) to explore a possible learning curve effect. Statistical significance was defined as P <.05. All statistical analyses were performed using Stata/ IC version 12.1 (College Station, TX).

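### The two documents name no single primary test for procedure time (Fisher's exact in the protocol, t or Mann-Whitney in the SAP), and neither adjusts it for the randomisation strata

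*Protocol*

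**What the plan says.** Procedure time is the only primary endpoint (protocol sections 1.2 and 2.B). It is an elapsed time, running from unpacking the needle to withdrawing it after the last marker.

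**Protocol, section 2.E, item ii.** Fisher's exact test is assigned to a list of comparisons between the arms that includes "procedure time, adverse event rate, rate of migration, ease of fiducial deployment, and visualization of needle and fiducials via EUS and CT by using Fisher's". The only exception that follows is "When data is ordinal, comparisons will be made using Mann-Whitney U test". Item i allows a choice of test, but for baseline data only: "For evaluation of the demographic data a Fisher's exact test or Mann-Whitney U test will be performed as applicable".

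**SAP.** Chi-square and Fisher tests are kept for categorical data. Continuous data get "Student t test or Mann-Whitney U test for continuous data". The threshold is "Statistical significance was defined as P <.05". The primary endpoint is not mentioned in connection with any test.

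**Randomisation, protocol section 2.E.** The scheme is "central block randomization (5 blocks of 4 per stratified arm at each center) stratified based on tumor location (head/neck vs. body/tail"), so both centre and tumour location are strata. Their only stated uses in the analysis are "Pre-established subgroup analysis was performed by tumor location (head/neck vs body/tail") in the SAP and "Descriptive comparison of outcomes across sites" in the protocol's list of secondary endpoints.

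**The concern.** The protocol gives the primary endpoint a test that cannot be applied to a continuous time without a cut-off, and it states none. The SAP replaces that test with two candidates and does not say which one decides the trial. With 40 patients the two can fall on opposite sides of 0.05. Which of them is more likely to miss a real effect depends on the shape of the times, which is not known in advance, so the choice should be fixed before the data are seen.

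The randomisration strata raise a separate, smaller matter. If centre or location predicts procedure time, balancing on them and then leaving them out of the comparison overstates the standard error and gives away power that the design had already secured.

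**Working it through.** **1. The plan's own figure.** The stated size is 20 per arm, with 80% power and two-sided alpha 0.05. No SD is given, so the figure can only be inverted. The standardised difference needed is (1.960 + 0.842) × √(2/20) = 0.886 by the normal formula, or d = 0.909 by the t distribution. On the log scale this implies an SD of |ln 0.6|/0.909 = 0.562 for a time ratio of 0.6, and |ln 0.4|/0.909 = 1.008 for a ratio of 0.4. The protocol's wording points to 0.6 and the SAP's, read literally, to 0.4. Both serve here only as a range.

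**2. How often the SAP's two tests disagree at P < .05.** Simulated trials, 20 per arm, distributions assumed:

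| Times | Calibration | Disagree |
|---|---|---|
| Normal | d = 0.909 | about 5.5% |
| Gamma, ratio 0.6 | CV 0.55 (raw t power 80.4%) | 8.1% |
| Gamma, ratio 0.4 | CV 0.9 (raw t power 84.4%) | 10.9% |
| Lognormal, ratio 0.6 | raw t power about 80% (log-SD about 0.53) | about 9% |
| Lognormal, ratio 0.4 | raw t power about 80% (log-SD about 0.85) | about 13-14% |
| Lognormal, ratio 0.6 | log-SD 0.562 | 10.8% |
| Lognormal, ratio 0.4 | log-SD 1.008 | 22.4% |

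The direction also changes. In the last row Mann-Whitney alone is significant in 19.7% of trials and t alone in 2.6%. With gamma times at ratio 0.4, t alone is significant in 8.9% and Mann-Whitney alone in 2.0%. Neither test is safer in general.

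**3. Type I error if the smaller P is always taken.** It is about 6-6.5% when the strata explain none of the variance, 4.3-4.8% when they explain 20% (R² = 0.2), and 2.6-3.4% at R² = 0.4.

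**4. Leaving out the strata.** With balanced strata, the arm difference has true variance (1 − R²) times what the unadjusted test estimates, so the effective critical value is 1.96/√(1 − R²).
- R² = 0.2: 1.96/√0.8 = 2.19, two-sided error 2.8%.
- R² = 0.4: 1.96/√0.6 = 2.53, two-sided error 1.1%.

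Simulation with two balanced strata gives the same 2.8% and 1.1%. With 3, 5 or 8 uneven centres (allocation assumed) the unadjusted error is 3.0-3.6% and 1.8-2.5%, against 4.6-5.2% adjusted.

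Power, log-scale t test, ratio 0.6, with 0.562 as the total log-SD:

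| Layout | R² = 0.2, unadjusted / adjusted | R² = 0.4, unadjusted / adjusted |
|---|---|---|
| Two balanced strata | 83% / 88% | 85% / 95% |
| 3 centres | 81.8% / 87.1% | 83.7% / 94.3% |
| 5 centres | 80.8% / 85.8% | 83.7% / 93.8% |
| 8 centres | 80.0% / 84.4% | 82.5% / 92.0% |

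The differences are about 4-6 points at R² = 0.2 (for example 87.1 − 81.8 = 5.3) and about 10 at R² = 0.4 (94.3 − 83.7 = 10.6; 92.0 − 82.5 = 9.5). Unadjusted power does not fall below 80% in any of these cases.

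**5. Cost of adjusting when R² = 0.** Unadjusted 79.7%, 79.8% and 79.6% against adjusted 79.0%, 78.3% and 77.0% for 3, 5 and 8 centres: losses of 0.7, 1.5 and 2.6 points.

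**The case against.** The Fisher entry looks like a careless list. The same sentence covers rating-scale items that the next sentence sends to Mann-Whitney, and under the SAP a continuous time cannot go to Fisher at all. That stands as an explanation, but the protocol text still needs correcting, and the SAP's replacement is still two tests.

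An unadjusted comparison of 40 patients spread over centre-by-location cells is also defensible. It does not inflate type I error, so the missing adjustment is a loss of efficiency and not an error. That stands too.

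A reader might draw four stronger conclusions, which the documents do not support:
- **That the primary test has only about half the intended power.** A Fisher test on time split at the pooled median has about 52% power, but neither document contains a median split.
- **That the trial falls below 80% power without adjustment.** Figures of 59-73% arise only if 0.562 is taken as a within-stratum SD. No passage suggests this, and an unadjusted two-sample calculation more naturally uses the total SD.
- **That the tests would typically disagree in a fifth of trials.** The 22.4% needs a log-SD of 1.008, a CV of about 133%. Against the 7-12 minute average in the protocol's background section, that is an SD of roughly 9-16 minutes. It comes from calibrating to a log-scale test that neither document mentions.
- **That the test was chosen after the results were seen.** The SAP's past tense does not show that the choice was made in advance, but neither does it show the reverse.

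Nor can both harms be pressed together. Inflation from choosing the smaller P needs strata that do not predict time, and lost power needs strata that do.

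**Conclusion.** The point holds, and its size is modest. The textual part is firm: the protocol's test for the primary endpoint is unusable as written, the SAP contradicts it and leaves two tests open, and neither document adjusts the primary comparison for the strata used in randomisation.

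The sizes rest wholly on assumed SDs, distributions, centre layouts and strata effects:
- The open choice could change the significance call in about 5-14% of trials for normal, gamma or lognormal times calibrated to about 80% raw t power. About 22% is an upper case for very skewed times.
- Type I error from choosing the smaller P is at most about 6-6.5%, and is not inflated if the strata matter.
- Omitting predictive strata makes the test conservative (about 3% at R² = 0.2, 1-2.5% at R² = 0.4) and forgoes about 4-6 or about 10 power points respectively. Planned power is kept if the design SD is the total SD.

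This should be fixed because the repair is cheap and concerns the one comparison that decides the trial.

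**What to change.** - Delete procedure time from the Fisher list in protocol section 2.E.
- Name one primary test of procedure time, in the same words in both documents, adjusted for tumour location and centre. Pool small centres by a rule that uses randomised counts only. A linear model with strata terms or a stratified rank test (van Elteren) would serve.
- A log scale with a ratio of geometric means and its 95% CI is an option, because the hypothesis is stated as a ratio of times. It is not a requirement, and statisticians may differ. In the simulated cases it cost about 5 to 11 power points against the raw t test with gamma times and gained about 6 to 19 with lognormal times.
- Report the other test as a sensitivity analysis that does not decide the result.

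The minimum repair is to name one of the SAP's two tests as primary. That removes the ambiguity but forgoes the adjustment.

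The cost is wording in both documents and one further analysis. No new data are needed: tumour location is on the data collection list and centre is known from randomisation. The downside is about 1-3 power points if the strata do not predict time. Because the SAP is written in the past tense, a change now would not create prespecification, and any new analysis should be labelled a re-analysis.
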